5.3.6. Supportive Analyses

5.3.6.1. Co-primary endpoint clinical remission at Week 12 based on alternative CDAI calculation approach

A supportive analysis of the endpoint of clinical remission at Week 12 will be performed, and it will use the same attributes as those for the co-primary estimand 1 defined in Section 5.3.2.1 However, the calculation of the CDAI will be based on the alternative approach specified in Section 5.3.1. If the CDAI is missing at Week 12, after accounting for the ICEs, nonresponder imputation will be used.

The co-primary endpoint of clinical remission at Week 12 will be compared between guselkumab induction dose group and placebo using the Estimand 1 and its associated estimator. The estimand will be estimated by the adjusted treatment differences between guselkumab and placebo in the

percentage of participants who achieve clinical remission at Week 12 and the associated 95% CI. Guselkumab versus placebo will be compared for the co-primary endpoint using a 2-sided Mantel-Haenszel test (Common Risk Difference Test) at a significance level of 0.05. Specifically, the adjusted treatment differences will be in terms of the common risk difference using Mantel-Haenszel stratum weights and the variance will be based on the Sato variance estimator. The stratification variables used are baseline CDAI score (\leq 300 or >300), baseline SES-CD score (\leq 12 or >12), and BIO-Failure status (Yes or No).

5.3.6.2. Co-primary endpoint endoscopic response at Week 12 based on baseline segments matched approach

A supportive analysis of the endpoint of endoscopic response at Week 12 will be performed, and it will use the same attributes as those for the co-primary estimand 2 defined in Section 5.3.2.1 However, the calculation of the SES-CD will be based on the alternative approach specified in Section 5.3.1 (ie, the baseline segments matched approach). If the SES-CD is missing at Week 12, after accounting for the ICEs, nonresponder imputation will be used.

The co-primary endpoint of endoscopic response at Week 12 will be compared between guselkumab induction dose group and placebo using the Estimand 2 and its associated estimator. The estimand will be estimated by the adjusted treatment differences between guselkumab and placebo in the percentage of participants who achieve endoscopic response at Week 12 and the associated 95% CI. Guselkumab versus placebo will be compared for the co-primary endpoint using a 2-sided Mantel Haenszel test (Common Risk Difference Test) at a significance level of 0.05. Specifically, the adjusted treatment differences will be in terms of the common risk difference using Mantel-Haenszel stratum weights and the variance will be based on the Sato variance estimator. The stratification variables used are baseline CDAI score (\leq 300 or >300), baseline SES-CD score (\leq 12 or >12), and BIO-Failure status (Yes or No).

5.4. Secondary Endpoints Analysis

5.4.1. Definition of Endpoints

The secondary endpoints are listed below.

- Clinical remission (CDAI score <150) at Week 24
- PRO-2 remission at Week 12 (defined as an AP mean daily score at or below 1 and SF mean daily score at or below 3, ie, AP ≤1 and SF ≤3, and no worsening of AP or SF from baseline)
- Clinical response (decrease from baseline in CDAI ≥100 points or clinical remission) at Week 12

5.4.2. Estimands

5.4.2.1. Estimands for the Secondary Endpoints

Secondary Estimand of Clinical Remission at Week 24 (Main Estimand 5)

The following describes the attributes of the Main Estimand 5.

Treatment by Week 24:

Experimental:

- Guselkumab ^{CCI} q4w (Weeks 0, 4, and 8) followed by guselkumab ^{CCI} q4w (Weeks 12, 16, and 20)
- Guselkumab ^{CCI} q4w (Weeks 0, 4, and 8) followed by guselkumab ^{CCI} q8w starting at Week 16

Control: Placebo SC q4w (Weeks 0, 4, 8, 12, 16, and 20)

Population: Participants with moderately to severely active Crohn's disease

Variable (Endpoint):

A binary response variable (response/nonresponse) where response is defined as achieving CDAI score <150 at Week 24 without experiencing any of the ICEs in categories 1, 2, 3, 5 and 6 as outlined below prior to the Week 24 visit.

Intercurrent events and corresponding strategies:

ICE Identifier	ICE Description	Corresponding Strategy
1	A Crohn's disease-related surgery (with the exception of minor procedures such as drainage of a superficial abscess or seton placement, etc.)	Composite
2	A prohibited change in Crohn's disease medication (See Appendix 2)	Composite
3	Discontinuation of study intervention due to lack of efficacy or an AE of worsening of Crohn's Disease	Composite
4	Discontinuation of study intervention due to COVID-19 related reasons (excluding COVID-19 infection) or regional crisis	Treatment Policy
5	Discontinuation of study intervention due to COVID-19 infection or for reasons other than those specified in ICE categories 3 and 4	Composite
6	Meets rescue criteria as determined by the IWRS	Composite

The composite strategy assesses the treatment effects not only based on the variable measurements, but also based on ICEs. This estimand acknowledges that having an ICE in categories 1-3, 5 and 6 is an unfavorable outcome. For participants experiencing ICE category 4, the treatment policy strategy considers the occurrence of ICE category 4 is irrelevant in defining the treatment effect.

Population-level summary:

Difference in proportions of responders (according to the **Variable** defined above) between each guselkumab group and the placebo group.

Secondary Estimand of PRO-2 Remission at Week 12 (Main Estimand 6)

The same estimand (except for the "Variable" attribute) that is specified for the co-primary endpoint analyses will be used.

Variable (Endpoint):

A binary response variable (response/nonresponse) where response is defined as achieving PRO-2 remission (defined as AP \leq 1 and SF \leq 3, and no worsening of AP or SF from baseline) at Week 12 without experiencing any of the ICEs in categories 1 to 3 and 5 as outlined above, prior to the Week 12 visit.

Secondary Estimand of Clinical Response at Week 12 (Main Estimand 7)

The same estimand (except for the "Variable" attribute) that is specified for the co-primary endpoint analyses will be used.

Variable (Endpoint):

A binary response variable (response/nonresponse) where response is defined as achieving clinical response (decrease in CDAI score ≥ 100 points or clinical remission) at Week 12 without experiencing any of the ICEs in categories 1 to 3 and 5 as outlined above, prior to the Week 12 visit.

5.4.2.2. Supplementary Estimands for the Secondary Endpoints

In these supplementary estimands, ALL intercurrent events defined above for the main estimands of the secondary endpoints are addressed by the **composite strategy**. The supplementary estimands for the secondary endpoints acknowledge that having an intercurrent event is an unfavorable outcome. The attributes of the supplementary estimands for the secondary endpoints are the same as those for the main estimands of the secondary endpoints with the exception of the **Variable**, which is described as follows:

Supplementary Estimand of Clinical Remission at Week 24 (Estimand 8)

Variable (Endpoint): A binary response variable (response/nonresponse) where response is defined as achieving CDAI score <150 at Week 24 without experiencing any of the ICEs in categories 1-6 prior to the Week 24 visit.

Supplementary Estimand of PRO-2 Remission at Week 12 (Estimand 9)

Variable (Endpoint): A binary response variable (response/nonresponse) where response is defined as achieving PRO-2 remission (defined as AP ≤ 1 and SF ≤ 3 , and no worsening of AP or SF from baseline) at Week 12 without experiencing any of the ICEs in categories 1-5 as outlined above, prior to the Week 12 visit.

Supplementary Estimand of Clinical Response at Week 12 (Estimand 10)

Variable (Endpoint): A binary response variable (response/nonresponse) where response is defined as achieving clinical response (decrease in CDAI score ≥ 100 points or clinical remission) at Week 12 without experiencing any of the ICEs in categories 1-5 as outlined above, prior to the Week 12 visit.

5.4.3. Analysis Methods

5.4.3.1. Estimator (Analysis) of the Secondary Endpoints

The analyses of the secondary endpoints will be based on the FAS, which includes all randomized participants who received at least 1 (partial or complete) dose of study intervention. Participants will be analyzed according to the intervention group to which they were randomized regardless of the study intervention they actually received.

Regarding the ICE strategies, for the treatment policy strategy, the associated ICE event will be ignored, and any data observed after the associated ICE event will be used for the analysis. After accounting for the treatment policy strategy, any missing data will be handled by the missing data rules described below.

For CDAI-related endpoints, if the CDAI score cannot be calculated at a visit, the CDAI score will be considered missing for that visit. Participants who have a missing CDAI score at a visit after accounting for the ICE strategies will be considered not to be achieving the endpoint involving that visit as measured by the CDAI score (ie, Nonresponder Imputation (NRI)).

Participants who have missing AP or SF scores at a visit after accounting for the ICE strategies will be considered not to be in PRO-2 remission for that visit.

Summaries of the proportion of participants that achieve each secondary endpoint and the associated 95% confidence interval by treatment group, along with the adjusted treatment difference between guselkumab group and the placebo group, as well as the associated 95% confidence interval, will be presented for each secondary endpoint. Guselkumab dose group (s) versus placebo will be compared for the secondary endpoints using a 2-sided Mantel Haenszel test (Common Risk Difference Test) at a significance level of 0.05. Specifically, the adjusted treatment differences will be in terms of the common risk difference using Mantel-Haenszel stratum weights and the variance will be based on the Sato variance estimator. The stratification variables used are baseline CDAI score (\leq 300 or >300), baseline SES-CD score (\leq 12 or >12), and BIO-Failure status (Yes or No).

5.4.3.2. Testing procedure

The Type I error rate will be controlled at the 0.05 (2-sided) significance level over the co-primary endpoints, secondary endpoints, and two Week 48 exploratory endpoints in the multiplicity-controlled testing procedure.

The testing procedure begins with a fixed-sequence testing procedure which will be used to control the overall Type 1 error rate at the 0.05 level across the co-primary and secondary endpoints listed below. The endpoints will be tested sequentially by the following prespecified order:

- 1. Clinical remission at Week 12 (co-primary)
- 2. Endoscopic response at Week 12 (co-primary)
- 3. Clinical remission at Week 24 compared between the high dose group (^{CCI} q4w) and the placebo group (secondary)
- 4. Clinical remission at Week 24 compared between the low dose group ^{CCI} q8w) and the placebo group (secondary)
- 5. PRO-2 remission at Week 12 (secondary)
- 6. Clinical response at Week 12 (secondary)

If any test in the sequence, including the tests of the co-primary endpoints, does not achieve significance at the 2-sided 0.05 level, the p-values for all of the subsequent endpoints will be considered nominal.

Two exploratory endpoints (clinical remission at Week 48, endoscopic response at Week 48) will be tested at the end of the fixed-sequence testing procedure above; the part of the testing procedure for these endpoints is described in Section 5.5.3. Other exploratory endpoints will not be multiplicity-controlled, and nominal p-values will be presented.

5.4.3.3. Estimator for the Supplementary Estimands of the Secondary Endpoints

The same estimators used for the secondary estimands will be used for the supplementary estimands, with the exception that the rules for treatment policy strategy no longer apply as all ICEs are addressed by the composite strategy. After accounting for the ICE strategies, participants whose responder status is missing for a secondary endpoint will be considered to be a nonresponder for that endpoint.

5.4.4. Subgroup Analyses

The consistency of treatment effect for the secondary endpoints will be evaluated for the subgroups of BIO-Failure, CON-Failure and BIO-Naïve using the secondary estimands defined in Section 5.4.2.1. The secondary estimator will be applied to each subgroup.

5.4.5. Supportive analyses

5.4.5.1. Secondary endpoint clinical remission at Week 24 based on alternative CDAI calculation approach

A supportive analysis of the endpoint of clinical remission at Week 24 will be performed, and it will use the same attributes as those for the secondary estimand 5 defined in Section 5.4.2.1 However, the calculation of the CDAI will be based on the alternative approach specified in Section 5.3.1. If the CDAI is missing at Week 24, after accounting for the ICE strategies, nonresponder imputation will be used.

5.4.5.2. Secondary endpoint clinical response at Week 12 based on alternative CDAI calculation approach

A supportive analysis of the endpoint of clinical response at Week 12 will be performed, and it will use the same attributes as those for the secondary estimand 7 defined in Section 5.4.2.1 However, the calculation of the CDAI will be based on the alternative approach specified in Section 5.3.1. If the CDAI is missing at Week 12, after accounting for the ICE strategies, nonresponder imputation will be used.

5.5. Exploratory Endpoints Analysis

Two exploratory endpoints (clinical remission at Week 48, endoscopic response at Week 48) will be controlled for multiplicity. These two endpoints will be tested after the testing of the secondary endpoints. See the description of the testing procedure later in Section 5.5.3. The testing of other exploratory endpoints will not be controlled for multiplicity, and nominal p-values will be provided.

5.5.1. Definition of Endpoints and Description of Scoring Systems

All definitions and explanation of scoring systems related to the exploratory endpoints are provided below.

5.5.1.1. Clinical

Abdominal Pain Numerical Rating Scale

The Numerical Rating Scale (NRS) for pain is a unidimensional measure of pain intensity in adults. An 11-point (0-10) NRS is used to evaluate abdominal pain. The score of 0 represents "no pain" and the score of 10 represents "pain as bad as you can imagine", with greater scores indicating greater pain severity and intensity. Participants will select only one number that best reflects their pain at its worst in the past 24 hours. The abdominal pain NRS will be assessed daily for 7 days prior to a scheduled assessment visit (and every day for 14 days prior to final efficacy & safety follow-up). The average over the 7 days prior to a visit will be used to determine the NRS score at that visit. Daily average abdominal pain NRS at a scheduled visit will not be calculated if total days of assessment is less than 4.

NCT05197049

AP Daily Score

Average daily abdominal pain score based on the CDAI is defined as the sum of abdominal pain/cramps ratings in the previous 7 days in a diary card divided by the total number of days assessments were performed. Average daily abdominal pain score at a scheduled visit will not be calculated if total days of assessment is less than 5.

SF Daily Score

Average daily stool frequency score based on the CDAI is defined as the sum of number of liquid or very soft stools in the previous 7 days in a diary card divided by the total number of days assessments were performed. Average daily SF score at a scheduled visit will not be calculated if total days of assessment is less than 5.

Bristol Stool Form Scale

The Bristol Stool Form Scale (BSFS) is a medical aid to classify the form (or consistency) of human feces into 7 categories as illustrated in Table 4. It has been used as a research tool to evaluate the effectiveness of treatments for various diseases of the bowel (eg, irritable bowel syndrome). Types 1 and 2 indicate constipation, with 3 and 4 being the ideal stools as they are easy to defecate while not containing excess liquid, 5 indicates lack of dietary fiber, and 6 and 7 indicate diarrhoea.

Table 4:Bristol Stool Form Scale

Type 1: Separate hard lumps, like nuts (difficult to pass) Type 2: Sausage-shaped, but lumpy Type 3: Like a sausage but with cracks on its surface Type 4: Like a sausage or snake, smooth and soft (average stool) Type 5: Soft blobs with clear cut edges Type 6: Fluffy pieces with ragged edges, a mushy stool (diarrhoea) Type 7: Watery, no solid pieces, entirely liquid (diarrhoea)

Average number of BSFS types 6 and 7 stools per day is defined as the sum of number of BSFS types 6 and 7 stools in previous 7 days in a dairy card divided by the total number of days assessments were performed. Similarly, average number of BSFS types 5, 6 and 7 stools per day is defined as the sum of number of BSFS types 5, 6 and 7 stools in previous 7 days in a dairy card divided by the total number of days assessments were performed.

Average number of BSFS stools per day at a scheduled visit will not be calculated if total days of assessment is less than 5 within the previous 7 days prior to a scheduled visit.

PRO-2 Remission

PRO-2 remission is defined as AP mean daily score at or below 1 (AP \leq 1) AND an SF mean daily score at or below 3 (SF \leq 3), and no worsening of AP or SF from baseline.

Corticosteroid-free Clinical Remission

Corticosteroid-free clinical remission is defined as CDAI score <150 and not receiving corticosteroids (at a specified visit).

90-day Corticosteroid-free Clinical Remission

90-day corticosteroid-free clinical remission is defined as achieving clinical remission and not receiving corticosteroids for 90 days prior to the specified visit e.g. 90-day corticosteroid-free clinical remission at Week 48 is defined as CDAI score <150 at Week 48 and not receiving corticosteroids for 90 days prior to Week 48.

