1.3. Schedule of Activities (SoA)

Table 1: Schedule of Activities: Screening Phase

Study Procedures	Screening (Within 5 weeks)	Notes
Administrative		
Informed consent	X	
Inclusion/exclusion criteria	X	
Medical history and demographics	X	
ECG	X	
Chest radio graph	X	Chest radiograph must be obtained within 12 weeks before the Week 0 visit. Note: A chest CT scan is also acceptable if obtained instead of a chest radiograph outside of the protocol.
TB evaluation/other infection assessment	Х	All participants will undergo TB testing within 2 months before the Week 0 visit. More information on TB evaluation is provided in Section 8.2.10 and inclusion criterion 9.
Stool studies to evaluate for enteric pathogens	X	Stool studies for enteric pathogens may be performed at screening at either the central or a local laboratory and must include a stool culture and Clostridioides difficile (formerly known as Clostridium difficile) toxin assay. Although stool studies may be processed at either the central or local laboratory, the central laboratory is preferred when available. Stool studies must have been performed within 4 months before Week 0. Additional testing, such as ova and parasites or Escherichia coli O157:H7 assessment, may be performed at the investigator's clinical discretion.
HBV and HCV testing	X	
HIV testing	X	
Provide Symptom and Health Diary (CDAI, BSFS, AP-NRS) and training	X	Provide participants with the take-home paper diary and provide training on diary completion. The diary information collected prior to the randomization visit will be used to calculate the CDAI, BSFS, and AP-NRS score at baseline (Week 0). A minimum of 7 days of CDAI data during the screening period is required to calculate the CDAI score at baseline (Week 0).
Schedule video ileocolonoscopy	X	During the initial screening visit the video ileocolonoscopy should be scheduled, if feasible. The screening ileocolonoscopy will be performed at least 10 days before but no more than approximately 3 weeks before the Week 0 visit to prevent interfering with the collection of CDAI data for the Week 0 visit.
Safety Assessments		
Physical examination	Х	A complete, detailed physical examination should be performed at the screening visit for study eligibility assessment.
Weight	X	
Height	X	
Vital signs	X	Temperature, pulse/heart rate, respiratory rate, and blood pressure
Serum pregnancy test	X	Must be performed in female participants of childbearing potential.

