Follicle stimulating hormone	X	Consider testing in women with no menses for ≥12 months without an alternative medical cause (see Section 10.8 for further guidance).

CONFIDENTIAL – FOIA Exemptions Apply in U.S. Status: Approved, Date: 04 October 2024

Study Procedures	Screening (Within 5 weeks)	Notes
C-SSRS	X	At the screening visit, the C-SSRS should be completed as the first assessment after signing informed consent and before any other tests, procedures, or other consultations to prevent influencing participant perceptions. The investigator or trained study site personnel will interview the participant and complete the C-SSRS.
Efficacy Assessments		
Fistula assessment	X	
Video ileocolonoscopy	X	To prevent interfering with the collection of CDAI data for the Week 0 visit, the screening ileocolonoscopy will be performed at least 10 days before but no more than approximately 3 weeks before the Week 0 visit.
Stool sample (fecal calprotectin)	X	If stool samples are collected around the time of the screening ileocolonoscopy, they must be collected before the start of the bowel preparation for ileocolonoscopy (through on-site or at-home collection).
CRP	X	
Clinical Laboratory Assessments		
Hematology and chemistry	X	
Pharmacodynamics and Biomarkers		
Ileocolonoscopy biopsy sample collections for histology	X	Refer to the biopsy manual for details on the biopsy sample collection.
Ileocolonoscopy biopsy sample collections for exploratory RNA and protein assessments (where local regulations permit).	X	Refer to the biopsy manual for details on the biopsy sample collection.
Ongoing Participant Review		
Concomitant therapy	X	Concomitant therapies should be documented after signing informed consent and should remain stable for the duration of the screening period (see Concomitant Therapy section).
Adverse events	X	The reporting of adverse events should begin after the informed consent is signed and should continue for the duration of the screening period.

Abbreviations: AP-NRS=Abdominal Pain-Numerical Rating Scale; BSFS=Bristol Stool Form Scale; CDAI= Crohn's Disease Activity Index; CRP=C-reactive protein; C-SSRS=Columbia-Suicide Severity Rating Scale; CT=computed tomography; ECG=electrocardiogram; HBV=hepatitis B virus; HCV=hepatitis C virus; HIV=human immunodeficiency virus; RNA=ribonucleic acid; TB= tuberculosis

Table 2: Schedule of Activities: Main Treatment Phase Weeks 0 to 24

Week ^{a,b} :	0	4	8	12	16	20	24	Notes
Study Procedures ^c								

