								CDAI: The most recent hematocrit value obtained during the screening window will be used to calculate CDAI at Week 0. For all other visits, the most recent hematocrit value obtained will be used to calculate the CDAI.
Weight	X	X	X	X	X	X	X	Weight measurement is used to support CDAI assessments, PK modeling, and safety.
Fistula assessment	X	X	X	X	X	X	X	

 $CONFIDENTIAL-FOIA\ Exemptions\ Apply\ in\ U.S.$

Week ^{a,b} :	0	4	8	12	16	20	24	Notes
Study Procedures ^c								
Video ileocolonoscopy				X				To prevent interfering with the collection of CDAI data, the video ileocolonoscopy must be performed at least 10 days before or at the designated visit (ie, Week 12). If performed on the day of the designated visit, the 7 days before the initiation of the ileocolonoscopy preparation should be utilized to calculate CDAI scores for these visits.
Stool sample (fecal calprotectin)	X	X	X	X			X	Week 0: Not required if sample already collected within 2 weeks of the Week 0 visit. Week 12: Stool sample collection (through on-site or at-home collection) must be obtained before the start of a bowel preparation if there is a coinciding ileocolonoscopy scheduled for that visit.
CRP	X	X	X	X	X	X	X	Week 0: Not required if sample already collected within 2 weeks of the Week 0 visit.
Patient-reported Outcomes								
IBDQ	X		X	X			X	IBDQ and PROMIS-29 should be administered before the C-SSRS and before any clinical
PROMIS-29	X		X	X			X	procedures or tests are performed. These assessments are completed by participants on-site using the provided tablet.
Clinical Laboratory Assessments								
Hematology and chemistry	X	X	X	X	X	X	X	Week 0: Laboratory tests are not required if screening laboratory tests were performed within 2 weeks of the Week 0 visit.
Pharmacokinetics and Immunogenicit	v							
Study intervention serum concentration	Х	X	X	X	X	Х	X	Blood samples should be collected before the administration of study intervention. All reasonable attempts should be made to collect samples at the scheduled time points and record the actual times of PK sample collections.
Assessment for antibody to study intervention	X	X	X	X			X	Blood samples should be collected before the administration of study intervention. All reasonable attempts should be made to collect samples at the scheduled time points and record the actual times of sample collections.
Pharmacodynamics and Biomarkers								

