infection assessment																			immediate and thorough investigation should be undertaken. More information on TB evaluation is provided in Section 8.2.10.
Injection-site evaluation	X	X	X	X	Х	Х	Т	Х	Т	X	Т	X	T	Х	Т	Х	Т	X	An injection-site reaction is any adverse reaction at an SC study intervention injection site. Injection sites will be evaluated for reactions, and any injection-site reaction will be recorded as an AE. Participants are trained to perform self-evaluation for injection-site reactions and reporting of AEs.
C-SSRS	X	Х	Х	Х	Х	Х		Х		Х		Х		Х		Х		Х	The C-SSRS should be completed after all PRO assessments and before any other tests, procedures, or other consultations to prevent influencing participant perceptions. The investigator or trained study site personnel will interview the participant and complete the C-SSRS.
Efficacy Assessmen	ts																		
Collect and review Symptom and Health Diary • CDAI • BSFS	X X	X X	X X	X X	X X	X X	Т	х	Т	x	Т	x	Т	х	Т	х	Т	X	Diary information should be completed daily, and participants should bring their diaries to each on-site visit. The daily diary includes patient-reported data for the CDAI, BSFS, and AP-NRS.
AP-NRS	X	X	X	X	X	X													Collection for BSFS and AP-NRS will conclude at Week 48.
																			The most recent hematocrit value obtained will be used to calculate the CDAI.
Weight	X	X	X	X	X	X	T ^f	X	T ^f	X	T ^f	X	T^{f}	X	Tf	X	Tf	X	Weight measurement is used to support CDAI assessments, PK modeling, and safety. Weight measurement is not required at visits performed via telemedicine contact.
Fistula assessment	X	X	Х	X	X	X	Tf	X	Tf	X	Tf	X	Tf	X	Tf	X	Tf	X	Assessment is not required at visits performed via telemedicine contact.
Video ileocolonoscopy						X												X	To prevent interfering with the collection of CDAI data, the video ileocolonoscopy must be performed at least 10 days before or at the designated visit (ie, Week 48 and Week 96). If performed on the day of the designated

Week ^{a,b} :	28	32	36	40	44	48°	52 ^d	56	60 ^d	64	68 ^d	72	76 ^d	80	84 ^d	88	92 ^d	96	Notes
Study Procedures ^e																			
																			visit, the 7 days before the initiation of the ileocolonoscopy preparation should be utilized to calculate CDAI scores for these visits.

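### For a same-day ileocolonoscopy at Week 12 or Week 48, bowel-preparation days are removed from the CDAI but left in AP-NRS and BSFS, and the rule for the AP and SF daily scores is unstated

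*SAP*

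**What the plan says.** Protocol Section 1.3, Table 2, gives two permitted timings for the Week 12 procedure: "the video ileocolonoscopy must be performed at least 10 days before or at the designated visit (ie, Week 12"). Table 3 does the same for Weeks 48 and 96. For the same-day option, the Table 2 note moves the diary window: "the 7 days before the initiation of the ileocolonoscopy preparation should be utilized to calculate CDAI scores for these visits". The Table 3 note has the same rule and again names only the CDAI: "ileocolonoscopy preparation should be utilized to calculate CDAI scores for these visits".

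BSFS and AP-NRS are kept in the same daily diary, through Week 48, but are not CDAI items. SAP 5.5.1.1 defines AP-NRS as follows: "The average over the 7 days prior to a visit will be used to determine the NRS score at that visit". It takes BSFS from the preceding seven diary days and does not calculate it if "total days of assessment is less than 5 within the previous 7 days prior to a scheduled visit". Neither definition mentions preparation.

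SAP 5.5.1.1 describes the AP and SF daily scores, which make up PRO-2, as derived from the CDAI. The SF score is the "sum of number of liquid or very soft stools in the previous 7 days in a diary card", divided by the number of days assessed. Preparation is not mentioned there either.

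At baseline the position is different. Table 1 says: "The screening ileocolonoscopy will be performed at least 10 days before but no more than approximately 3 weeks before the Week 0 visit". The Week 0 diary week therefore contains no preparation.

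**The concern.** The protocol moves the CDAI window because it accepts that preparation disturbs the diary. The same days disturb BSFS (liquid stools) and AP-NRS (cramping), yet those two scores keep the window that ends at the visit. The endpoints in SAP 5.5.2.9 (change from baseline, a reduction of at least 2 type 6-7 stools per day, a 3-point AP-NRS reduction) then compare a clean baseline week with a week that may include preparation. They also compare poorly with neighbouring visits that have no procedure.

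The AP and SF daily scores carry more weight. PRO-2 remission at Week 12 is test 5 of 6 in the fixed sequence (SAP 5.4.3.2). If it fails, clinical response at Week 12 becomes nominal. The Week 48 Hochberg tests are then not reached, because SAP 5.5.3 requires all six p-values to be below 0.05. A score that feeds this gate should have one defined set of diary days.

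**Working it through.** **Step 1: the windows side by side.**

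| Score | Diary window as written | Exception for preparation |
|---|---|---|
| CDAI | Preceding seven days (form in protocol Appendix 8) | Yes, notes to protocol Tables 2 and 3 |
| AP-NRS | Seven days up to the visit (SAP 5.5.1.1) | None |
| BSFS | Preceding seven days, minimum-day count run back from the scheduled visit (SAP 5.5.1.1) | None |
| AP and SF daily scores | Preceding seven days of the diary card, described as CDAI-derived (SAP 5.5.1.1) | Not stated; possibly inherited |

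**Step 2: when it bites.** A procedure at least 10 days before the visit leaves its preparation outside a seven-day window. Only the same-day option puts preparation inside it. BSFS and AP-NRS stop at Week 48, so their exposed visits are Weeks 12 and 48. Any exposure of AP and SF would extend to Week 96.

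**Step 3: how far a score can move.** The documents give no figure here to reproduce. With k preparation days in the window, usual daily value u and preparation-day value p:

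observed mean = ((7 − k)u + kp)/7, so rise = k(p − u)/7.

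The values of k, u and p, and the baselines used below, are assumptions. The thresholds are from SAP 5.5.2.9 and 5.4.1.

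- BSFS types 6-7, u = 1, p = 5 to 15. For k = 1 the rise is 4/7 = 0.57 to 14/7 = 2.00. For k = 2 it is 8/7 = 1.14 to 28/7 = 4.00. Example: with a baseline of 4 per day, the true reduction is 4 − 1 = 3, a responder. One preparation day of 10 gives (6×1 + 10)/7 = 2.29, a reduction of 1.71, a non-responder.
- AP-NRS, u = 2, p = 4 to 6. For k = 1 the rise is 2/7 = 0.29 to 4/7 = 0.57. For k = 2 it is 4/7 = 0.57 to 8/7 = 1.14. Example: with a baseline of 5, the true reduction is 3. One day rated 6 gives (6×2 + 6)/7 = 2.57, a reduction of 2.43, below the 3-point threshold.
- SF, only if preparation days count: u = 2, k = 1, p = 10 gives (6×2 + 10)/7 = 3.14, which fails the limit of 3. The pre-preparation week gives 2.00, which passes. At u = 2, one preparation day breaks the limit above 21 − 12 = 9 stools.
- AP, on the same condition: u = 1 and one day rated 2 or 3 gives 8/7 = 1.14 or 9/7 = 1.29, which fails the limit of 1.

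**Step 4: effect between arms.** Treatment is blinded and preparation should affect the arms alike. If it adds the same amount in each arm, the shift cancels from the difference in mean change. If instead p is the same for everyone, the mean difference among same-day participants shrinks by k/7 (14% for one day, 29% for two). Responder differences are diluted because true responders near the threshold are scored as failures.

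**The case against.** The strongest counter-argument concerns PRO-2. A reader might infer that preparation days are counted in the AP and SF daily scores, so that PRO-2 remission at Week 12 is contaminated and rests on different days from CDAI remission. The documents do not support that. Protocol Section 8.1 defines PRO-2 as the CDAI's own stool and pain items, unweighted, and the SAP calls both scores CDAI-derived. The CDAI form in Appendix 8 also refers to the preceding seven days, yet Tables 2 and 3 move its window. That wording alone therefore does not show that preparation days count. Nor is SAP silence decisive, because the SAP does not restate the preparation rule for the CDAI either. This stands: contamination of test 5 is not established.

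The inherited reading is not secured, however. SAP 5.3.1 points to Appendix 8, which carries no exception, so someone programming from the SAP would not meet the rule. SAP 5.5.2.4 ties two CDAI-based endpoints (no abdominal pain, and SF remission) to the week leading up to the visit. Taken literally, one preparation day rated 1 for pain gives 1/7 = 0.14 and fails the zero-pain endpoint.

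The second argument is that what remains is small. BSFS and AP-NRS are exploratory with nominal p-values, the exposure needs a same-day procedure, it occurs at two visits, and the expected effect is conservative. All of that stands and limits the weight of the point. It does not remove it: for these two scores the written rules, followed as they are, include preparation days.

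**Conclusion.** The point holds for AP-NRS and BSFS. At a Week 12 or Week 48 visit with a same-day ileocolonoscopy, the stated windows bring preparation days into the score, while baseline is free of them. The likely result is understated improvement within each arm and diluted responder differences. Nothing suggests that one arm is favoured or that a false positive is more likely.

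For the AP and SF daily scores, and so PRO-2 remission at Week 12, the finding is an ambiguity that should be settled because of its place in the testing sequence.

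No overall size can be given. A reader might be tempted to put a percentage on PRO-2 remitters lost. That would need the same-day share, the extra stools per preparation day and the spread of SF among remitters, none of which is in the documents, and it would also presuppose the literal reading. The shifts in the working show only that one or two preparation days can move a score by an amount comparable with the BSFS responder threshold, and by less relative to the AP-NRS threshold.

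**What to change.** Add one sentence to SAP 5.5.1.1: at any visit with a same-day ileocolonoscopy, all diary-based scores (AP and SF daily scores and hence PRO-2, AP-NRS, BSFS) use the same seven diary days as the CDAI, namely those before preparation starts, and the minimum-day counts (4 for AP-NRS, 5 for the others) apply to that window. The week-based wording in SAP 5.5.2.4 should be read the same way.

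The cost is small. The diary is completed daily, and the CDAI rule already needs the preparation start date. No protocol amendment is required, because protocol Section 9.4.1 lets the SAP clarify or modify the planned analyses. If the programming already works this way, the sentence documents it; if not, it corrects it.
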